13.11 CLINIC FOLLOW UP VISIT (30 ± 7 DAYS)

The subject will return to the clinic at one month (30 ± 7 days) and Study subjects will undergo the following clinical evaluation:

- Assessment of the ischemic/angina status (CCS, Braunwald or silent ischemia)

- Monitoring and documentation of adverse and serious adverse events,
- Documentation of any change to anti-platelet/anti-coagulant medical therapy.

An electrocardiogram will be repeated during the clinic visit as per the investigator's discretion.

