	Clinic follow up visit	30 ± 7 days
	Protocol guided follow-up of patient is vital; Investigators and Site study management team should ensure minimizing follow up lapses and to avoid subjects becoming Lost-To-Follow-Up.	
Study Procedure/ Methodology	Each subject will be followed from enrollment through 30 days ± 7 days for the effectiveness and safety endpoints.	

Spectranetics Corporation

Study Protocol Number: ELCA-1016

Version 1.0

Dated: 12 Oct 2016

	
Upon enrollment after obtaining a written informed consent, each patient will be assigned a unique identification number. Only patients eligible to undergo cardiac catheterizations as per routine practice will be considered for the study. Premedication of patients will be as per the investigator's routine practice. All patient data will be recorded on patient data forms.
 
Screening: This will be performed prior to the cardiac catheterization procedure. Only patients who have consented and fulfill the selection criteria will be enrolled. Additionally, ECG and Echocardiogram will be done using hospital equipment to ensure fulfillment of inclusion/exclusion criteria.
 
Procedure: The entire procedure will be carried out as per the site routine practice and the device will be used as per the IFU.
 
Clinic follow up visit (30 ± 7 days): The subject will return to the clinic at 1 month to evaluate angina status as per the CCS classification, AE assessments, concomitant medications and any coronary intervention that has occurred since the previous contact. An electrocardiogram (ECG) will be repeated during the clinic visit.

Key Inclusion Criteria
	
The subjects have to meet the following inclusion criteria:
 
 • Patient 18 years to 75 years, both inclusive • Have at least one severe stenotic lesion (greater than or equal to 80% diameter stenosis as assessed by visual estimation) • Hemodynamically stable patients coming to the site for cardiac catheterization and angiography who fulfill all the following criteria: 
 ▪ Have no clinically significant cardiac arrhythmias, based on ECG results ▪ Have no evidence of valvular pathology, based on echocardiogram results ▪ Have $\geq 30\%$ left ventricular ejection fraction

Spectranetics Corporation

Study Protocol Number: ELCA-1016

Version 1.0

Dated: 12 Oct 2016

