8. STUDY PROCEDURE OVERVIEW

Procedure		Screening (Day -10 to 0)	Coronary Atherectomy	Post Procedure Assessment	30 Days Clinic Follow Up (± 7 Days)	Unscheduled Visit
Informed Consent Signed		X				
Assessment of Eligibility Criteria		X				
Review of Medical History		X				
Review of Concomitant Medications		X	X	X	X	X
Physical Exam	Complete	X				X
	Angina Class (CCS)	X			X	X
	Vital Signs	X		X	X	X
Clinical Laboratory	Chemistry ¹	X ²				
	Cardiac Biomarkers (CK, CK-MB and Trop I)	X ³		X ⁵ , X ⁶		
	Pregnancy Test	X ⁹				
12 Lead Electrocardiogram (ECG)		X ³		X ⁴	X ⁷	X
LVEF measured through the Echo or LV Angiogram		X ²				
Coronary Angiogram		X				X ⁸
Device evaluation by Investigators				X		
Adverse Event Assessment			X	X	X	X

1	Blood chemistry includes Complete Blood Count (CBC) and platelet count, serum sodium, potassium, urea, creatinine, and Random Blood Sugar (RBS)
2	72 hrs prior to the index procedure.
3	24 hours prior to index procedure.
4	24 hours post procedure
5	6 - 24 hours post-procedure or at discharge whichever is earlier.
6	Cardiac Markers: If cardiac biomarkers (CK-MB or Trop I) > 3 time Upper Limit of Normal (ULN) or SAT, CK, CK-MB & Trop I post procedure, the levels must be evaluated every 8 hours until it returns to normal or until hospital discharge.
7	ECG: To be obtained for any suspicious episode of coronary ischemia or SAT during the baseline hospitalization.
8	If angiogram is performed during the unscheduled visit, may be collected.
9	Urine Pregnancy Test to be performed only for women of child bearing potential, within 72 hours before angiography

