12.5 STUDY ENDPOINTS

Efficacy Endpoint:

- Device Success: Successful crossing of the ELCA Catheter across the entire length of the stenotic lesion
- Procedural Success: Target lesions with less than 50% residual stenosis after laser and adjunctive therapy

Safety Endpoint:

- Freedom from major adverse cardiac events (MACE) through hospital discharge and at one month
MACE is defined as Death, Non-Q-wave and Q-wave myocardial infarction (MI), Target Lesion Revascularization, Cardiac Tamponade and Life-threatening arrhythmias
- TIMI Flow
- Lesion Morphology
- Device-related complications
- Procedure-related complications

In order to fully characterize the procedure, information of all treated lesions will be collected irrespective of whether the lesion has been treated with ELCA[®] product.

Electronic Case Report Forms will be utilized to collect relevant information.

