13.9 POST PROCEDURE ASSESSMENT (UNTIL DISCHARGE)

The index procedure will be considered as complete, when the guiding catheter has been removed from the subject and the subject has left the cardiac catheterization laboratory. If a guiding catheter is reinserted thereafter, it will be considered as a re-intervention. Relevant CRF will be completed for such re-intervention. Following post procedure parameters will be assessed after the Coronary Atherectomy:

1. Vital Signs

Subject's vitals will be assessed immediately post PCI as per the Investigator's discretion.

2. Laboratory Evaluation

Cardiac biomarkers (CK, CK-MB and Trop I) will be performed 06-24 hours / or at discharge of post-procedure whichever is earlier. If the cardiac biomarkers (CK-MB or Trop I) are 3 times above the upper limit of normal or in case of Sub Acute Thrombosis (SAT), CK, CK-MB & Trop I must be evaluated every 8 hours until it returns to normal or until hospital discharge.

3. Electrocardiogram

12-lead electrocardiogram will be obtained 24 hours post procedure. Electrocardiograms should also be obtained for any episodes suspicious for coronary ischemia or SAT during the baseline hospitalization.

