15. STATISTICAL ANALYSIS

As per the 25th SEC (Cardiovascular & Renal) meeting which deliberated the proposals on 30-10-2015 and recommended the firm (Spectranetics Corporation - Sponsor) shall conduct a Bridging study in Indian Population at least 25 patients. The directorate suggested that the sponsor submit a protocol for the study in India for clinical trial approval. Considering the 5 dropouts, Sponsor has set up this protocol to conduct the Excimer Laser Coronary Atherectomy (ELCA[®]) study in India on 30 eligible patients.

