16.8 PROTOCOL DEVIATIONS

Protocol deviations are defined as instances where protocol requirements are not followed in such a manner whereby data is unusable or unavailable.

Protocol deviations are less serious in nature and do not require IRB/IEC notification, as long as they do not have an effect on the rights, safety or welfare of the study subjects.

Protocol deviations include, but are not limited to:

- Procedure not performed within the allowed follow-up window
- Required data not obtained
- Follow-up procedure performed at an unapproved location

The study site should report the protocol deviation on the applicable CRF.

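### The 30-day ECG is unconditional in the synopsis, discretionary in 13.11 and wrongly footnoted in the schedule, so silent Q-wave MI may be unevenly captured in one-month freedom from MACE

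*Protocol*

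**What the plan says.** Three places in the protocol govern the ECG at the 30 ± 7 day visit.

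- **Section 6, synopsis:** "An electrocardiogram (ECG) will be repeated during the clinic visit". No condition is attached.
- **Section 13.11:** "An electrocardiogram will be repeated during the clinic visit as per the investigator's discretion".
- **Section 8, schedule:** the 30-day ECG cell is marked, with footnote 7. That footnote reads "ECG: To be obtained for any suspicious episode of coronary ischemia or SAT during the baseline hospitalization".

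Section 13.9, on assessment up to discharge, has almost the same sentence as footnote 7: "Electrocardiograms should also be obtained for any episodes suspicious for coronary ischemia or SAT during the baseline hospitalization".

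The endpoint concerned is freedom from MACE, assessed to discharge and at one month (Section 12.5): "MACE is defined as Death, Non-Q-wave and Q-wave myocardial infarction (MI"), followed by target lesion revascularisation, tamponade and life-threatening arrhythmia. Cardiac biomarkers are scheduled at screening and after the procedure only (Sections 8 and 13.9). The scheduled post-procedure ECG is at 24 hours. Section 16.8 lists "Required data not obtained" among protocol deviations.

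**The concern.** The same assessment at the same visit is required in one place and apparently optional in another. It bears on a named safety endpoint.

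The component at risk is narrow: Q-wave MI without symptoms that arises after the 24-hour ECG. If the investigator decides who has the 30-day ECG, such an event is found only in those selected. The study is open-label and single-arm, with up to five sites, so the share of subjects tested may vary by site and investigator. The error has one direction: an event that is not looked for is counted as freedom from MACE.

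There is also a conduct problem that does not depend on any MI being missed. A missing 30-day ECG is a deviation if the synopsis governs and is not one if 13.11 governs. Section 16.2 calls for full source verification of primary and secondary endpoint data, and a monitor cannot tell from the protocol whether this item is due.

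**Working it through.** **1. What each source requires at 30 days**

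| Source | 30-day ECG |
|---|---|
| Synopsis (Section 6) | Every subject |
| Section 13.11 | At the investigator's discretion |
| Schedule (Section 8), cell as marked | Scheduled |
| Schedule, footnote 7 on that cell | Only for suspected ischaemia or subacute thrombosis during the index admission |

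Footnote 7 cannot apply to a clinic visit at day 30 ± 7. It matches the in-hospital sentence of 13.9, so the marker appears to belong to the post-procedure ECG cell, which carries footnote 4. If it is removed from the 30-day cell, a plain scheduled ECG remains. That agrees with the synopsis and still conflicts with 13.11. The conflict therefore does not depend on how the footnote is read.

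**2. What else could detect an MI after the 24-hour ECG**

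- Symptomatic MI: the angina and adverse event assessments in 13.11, the ECG at unscheduled visits (Section 8) and the request for outside medical records (13.13).
- Biomarkers: none scheduled at 30 days.
- Silent Q-wave MI: only the 30-day ECG, among scheduled tests. Section 13.11 mentions silent ischaemia as part of ischaemic status but names no required test for it.

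**3. The plan's own figure**

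Section 15 records the regulator's recommendation that the sponsor "shall conduct a Bridging study in Indian Population at least 25 patients", plus 5 for dropouts: 25 + 5 = 30. This reproduces the planned 30. The protocol states no performance goal, alpha or power to reproduce.

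**4. Weight of one missed event**

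The change in the rate is 1/n when one otherwise event-free subject has an undetected MI:

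- n = 30: 1/30 = 3.3 percentage points
- n = 25: 1/25 = 4.0 percentage points

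Exact (Clopper-Pearson) two-sided 95% intervals for freedom from MACE follow. With no events, the lower limit is 0.025^(1/n).

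| n | Event-free | Rate | 95% interval |
|---|---|---|---|
| 30 | 30 | 100% | 88.4% to 100% |
| 30 | 29 | 96.7% | 82.8% to 99.9% |
| 25 | 25 | 100% | 86.3% to 100% |
| 25 | 24 | 96.0% | 79.6% to 99.9% |

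Missing one event moves the lower limit by 88.4 − 82.8 = 5.6 points at n = 30 and by 86.3 − 79.6 = 6.7 points at n = 25.

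**5. Can the bias itself be sized?**

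Not from the protocol. It gives neither a rate q of silent Q-wave MI nor a share f of subjects who would go without the ECG. As an illustration only, the chance of at least one missed event is 1 − (1 − qf)^n. With assumed q from 1% to 5% and f from 25% to 100%, this runs from 7% to 79% at n = 30 and from 6% to 72% at n = 25. A range that wide shows that the size is unknown, and the conclusion does not rest on it.

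**The case against.** The strongest points on the other side are these.

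- **13.11 may not make the ECG optional.** Its sentence says the test will be done before adding the discretion clause. Section 13.9 attaches the same clause to post-procedure vital signs, which the schedule marks without qualification. The clause could concern timing or manner. This stands as a reading. It makes 13.11 ambiguous, but a site may just as reasonably read it as permission to omit the ECG.
- **Two sources against one.** With the footnote set aside, the schedule supports the synopsis. True, and it supports the direction of the fix. It does not remove the conflicting sentence from the section that sites follow for this visit.
- **Silent ischaemia may be only one of several alternative classifications in 13.11.** That is a fair reading, and the conclusion does not need this phrase.
- **MI has no diagnostic criteria in the protocol.** Whether a new symptomless Q wave at day 30 counts as MACE is not stated, and a day-30 ECG does little for non-Q-wave MI. Both stand. The bias argument assumes that such a Q wave would count.
- **The intervals change no decision.** With no performance goal stated, the shift in the lower limit crosses no threshold. This stands: the figures show the weight of one event, not the size of the bias.
- **No between-site comparison is planned,** so uneven ascertainment matters only through the overall rate. Agreed. The effect is a possible upward shift in that one rate.

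**Conclusion.** The concern holds. The synopsis and 13.11 conflict on whether the 30-day ECG is required, and the schedule attaches to it a footnote that cannot apply. As a result, one-month freedom from MACE has no consistently required objective test for MI after the 24-hour ECG.

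The consequence is limited to clinically silent Q-wave MI in that interval and could only inflate freedom from MACE. It rests on the assumption that a new Q wave found at 30 days would be counted as MI. The total bias cannot be derived from the protocol; the weight is 3.3 points per missed event at 30 subjects and 4.0 at 25. The textual conflict is certain; the bias is possible. An analysis plan cannot repair this, because it cannot supply ECGs that were never recorded. The change should be made, though it does not call the whole design into question.

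**What to change.** 1. Reconcile the synopsis, Section 8 and 13.11 to one endpoint-recording rule: the 30-day ECG is recorded for every subject, as the synopsis already states and the schedule already marks. This concerns endpoint data only; it does not touch ECGs that an investigator orders for clinical reasons.
2. In Section 8, move footnote 7 from the 30-day ECG cell to the post-procedure ECG cell, beside footnote 4, to match 13.9.
3. Report the number of subjects without a 30-day ECG alongside freedom from MACE.

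**Cost:** one sentence in 13.11 and one footnote marker. Because the change to 13.11 is more than administrative, Section 16.9 would call for a written amendment approved by the sponsor, the ethics committees and, where required, the national regulator. In conduct, it means a few more ECGs than under 13.11, at a visit subjects already attend, and possibly a slightly lower reported rate of freedom from MACE.

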13.12 UNSCHEDULED CLINIC VISIT

If the subject is seen by the investigator between scheduled follow-up visits (not a study required visit), unscheduled follow-up CRF must be completed. The subject will still be required to come for the next scheduled follow-up visit if the unscheduled visit is out of the compliance follow-up window. If the subject has complications attributable to the study procedure and seeks medical advice from the Investigator between scheduled follow-up visits, an Event Reporting CRF must be completed in addition to a Follow-up CRF.

13.13 UNSCHEDULED CORONARY INTERVENTION

The indication for an unscheduled coronary intervention could be an abnormal electrocardiogram, positive exercises test, raised biomarkers or symptoms suggestive of coronary ischemia. Symptoms, stress testing and other appropriate evidence should be documented on the relevant CRF. In case of an unscheduled coronary angiogram in the follow up period during the study participation, the event must be reported on the relevant CRF.

If the subject is treated by a health-care professional other than the study investigator for treatment related to complications, the investigator must request copies of the medical records and, if necessary, complete an Event Reporting CRF.

13.14 SUBJECT LOST TO FOLLOW-UP

Subjects who do not complete the scheduled follow-up visits and have not officially withdrawn from the study are considered lost to follow-up. If a subject is lost to follow-up, an End of Study CRF must be completed and sent to the Sponsor/CRO as soon as possible, after subject status has been determined. If a subject fails to comply with follow-up evaluations, the study site must make repeated attempts (minimum three attempts) to contact the subject. Each attempt to contact the subject and the method used to contact (e.g., telephone contact, registered letter), must be documented in the subject's records.

13.15 EARLY DISCONTINUATION OF STUDY

The study may be discontinued/ terminated at any time at the request of the Sponsor, the Ethics Committee, Principal Investigator or Regulatory Authority, with appropriate and timely notification to all parties concerned, otherwise, the study is terminated upon completion of all enrolled subjects through one month (30±7 days) of clinic/angiographic follow-up.

13.16 STUDY EXIT

Every subject should be encouraged to remain in the study until they have completed the CIP required follow-up period of one month (30±7 days). If a subject prematurely discontinues the study, the reason for discontinuation should be documented in Case Report Form (CRF). Possible reasons for premature discontinuation may include, but are not limited to the following:

- For any reason determined by judgment of the investigator that the subject should no longer participate in this trial.
- Subject non-compliance with the CIP
- Subject lost to follow-up.
- Voluntary decision by the subject.
- Death

13.17 STUDY COMPLETION

Subject who completes all protocol-required study procedures.

13.18 DATA COLLECTION AND FOLLOW-UP FOR WITHDRAWN PATIENTS

Investigator will have to follow the patient who has been withdrawn from the study. Investigator should try to obtain the reason, if patient withdraws his/her consent. Reason for withdrawal from the study shall be documented, whenever possible. It is vital to collect safety data on any patient discontinued because of an adverse event (AE) or serious adverse event (SAE). In any case, every effort must be made to undertake protocol-specified safety follow-up procedures. If voluntary withdrawal occurs, the patient should be asked to continue scheduled evaluations, complete an end-of-study evaluation, and be given appropriate care under medical supervision until the symptoms of any AE resolve or the subject's condition becomes stable.

14. ADVERSE EVENT & DEVICE DEFICIENCIES

During the course of this clinical investigation adverse events (AE) might occur.

Adverse event information will be collected throughout the clinical investigation in the CRF by the investigator or designee.

Any adverse event will be followed until study end.

14.1 ADVERSE EVENT DEFINITION AND CLASSIFICATION

Adverse Events are defined and classified in this section according to the current version of ISO 14155.

[figure not shown]

Figure 4 – Adverse event definition and classification

Adapted from ISO 14155

Spectranetics Corporation

Study Protocol Number: ELCA-1016

Version 1.0

Dated: 12 Oct 2016

AE – Adverse event:

Any untoward medical occurrence, unintended disease or injury, or untoward clinical signs (including abnormal laboratory findings) in subjects, users or other persons, whether or not related to the investigational medical device.

Note: This definition includes events related to the investigational medical device

Note: This definition includes events related to the procedures involved

Note: For users or other persons, this definition is restricted to events related to investigational medical devices

ADE – Adverse Device Effect:

An *adverse event* related to the use of an investigational medical device.

Note: This definition includes adverse events resulting from insufficient or inadequate instructions for use, deployment, implantation, installation, or operation, or any malfunction of the investigational medical device.

Note: This definition includes any event resulting from use error or from intentional misuse of the investigational medical device.

SAE – Serious Adverse Event:

An *adverse event* that

- a) led to death,
- b) led to serious deterioration in the health of the subjects, that either resulted in
 - 1) a life-threatening illness or injury, or
 - 2) a permanent impairment of a body structure or a body function, or
 - 3) in-subject or prolonged hospitalization, or
 - 4) medical or surgical intervention to prevent life-threatening illness or injury or permanent impairment to a body structure or a body function,
- c) led to foetal distress, foetal death or a congenital abnormality or birth defect

Note: Planned hospitalization for a pre-existing condition, or a procedure required by the CIP, without serious deterioration in health, is not considered a serious adverse event.

SADE – Serious Adverse Device Effect:

An *adverse device effect* that has resulted in any of the consequences characteristic of a serious adverse event.

USADE – Unanticipated Serious Adverse Device Effect:

Serious adverse device effect which by its nature, incidence, severity or outcome has not been identified in the current version of the risk analysis report.

Note: Anticipated serious adverse device effect (ASADE) is an effect which by its nature, incidence, severity or outcome has been identified in the risk analysis report.

Device Deficiencies

Inadequacy of a medical device with respect to its identity, quality, durability, reliability, safety or performance.

Note: Device deficiencies include malfunctions, use errors and inadequate labelling.

Use error

Act or omission of an act that results in a different medical device response than intended by the manufacturer or expected by the user.

Note: Use error includes slips, lapses, and mistakes.

Note: An unexpected physiological response of the subject does not in itself constitute a use error. [ISO 14971:2007, definition 2.27]

14.2 ADVERSE EVENT REPORTING

Adverse events have to be reported in accordance to ISO14155 (current version), Schedule Y and all applicable amendments (Drugs and Cosmetics Rules, 1945), GCP for Clinical Research in India (2001, CDSCO), ICMR guidelines for Biomedical Research on Human Subjects (2006).

An adverse event occurring within this clinical trial will only be reported for enrolled subjects, as defined above.

Reporting of adverse events for enrolled subjects will be conducted until either study exit or study completion.

Spectranetics Corporation

Study Protocol Number: ELCA-1016

Version 1.0

Dated: 12 Oct 2016

According to ISO14155 (current version), the investigator shall:

- Record every adverse event and observed device deficiency, together with an assessment
- Report to the sponsor or designee, without unjustified delay, all serious adverse events and device deficiencies that could have led to a serious adverse device effect; this information shall be promptly followed by detailed written reports
- Report to the IRB/IEC serious adverse events and device deficiencies that could have led to a serious adverse device effect, if required by national regulations or IRB/IEC
- Report to regulatory authorities serious adverse events and device deficiencies that could have led to a serious adverse device effect, as required by national regulations.
- Supply the sponsor, upon sponsor's request, with any additional information related to the safety reporting of a particular event.

Adverse events classified to be serious and/or with a relation to the investigational device have to be reported to Spectranetics Corporation/CRO without unjustified delay after awareness by the investigator or by the investigator's designee.

Reporting should be done using the Adverse Event Form in the CRF. This report should deliver any information available at the time of reporting. Utmost effort has to be made to collect as much information as possible during initial reporting. Follow-up information has to be delivered as fast as possible to ensure timely completion of the report.

The investigator is obliged to provide copies of blinded source documents from the medical record, for all SAEs and ADEs, as requested by Spectranetics Corporation/CRO. Angiographic films and technical worksheets must be sent to Spectranetics Corporation/CRO by courier within 5 business days after assessment.

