13. CLINICAL INVESTIGATION PROCEDURES

Up to 30 subjects with documented clinical symptoms, ECG changes and study lesion identified by angiography requiring Coronary Atherectomy will be enrolled in this study.

A written informed consent form will be obtained for enrollment. Each patient will be assigned a unique identification number. Only patients eligible to undergo cardiac catheterizations as per routine practice will be considered for the study. Premedication of patients will be as per the investigator's routine practice. All data will be captured in Case Record Form.

13.1 SCREEN FAILURE:

There may be a provisionally enrolled subject who withdraws consent prior to the index procedure or is unsuitable for the Excimer Laser Coronary Atherectomy (ELCA[®]) following laboratory assessments, pre-procedure ECG or any study specific invasive or non-invasive treatment as pre-specified in the Clinical Investigation Plan. These subjects will be exited from the study once screen failure is confirmed. Subject informed consent forms will be kept in the site's administrative files. These subjects will not be considered as part of the 30 patients for the analysis.

13.2 ENROLLED:

The investigator must ensure that all patients being considered for the study meet the study criteria (all of the inclusion and none of the exclusion criteria). The investigator should apply no additional exclusions, in order that the study population will be representative of all eligible patients. Patient selection is to be established by checking through all inclusion/ exclusion criteria at screening and baseline. A relevant record (e.g. checklist) must be stored with the source documentation at the study site. Deviation/Violation from any entry criterion excludes patients from enrollment into the study.

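### Section 14.2 stops adverse event reporting at study exit, while 13.18 requires continued safety follow-up and 14.8 has no exit cut-off, so some one-month MACE in early exits could go unreported

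*Protocol*

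**What the plan says.** Section 14.2 sets the reporting window: "Reporting of adverse events for enrolled subjects will be conducted until either study exit or study completion". The two end points are described in section 13:

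- **Completion (13.17):** "Subject who completes all protocol-required study procedures".
- **Exit (13.16, headed Study Exit):** the section concerns leaving before the one-month visit. "If a subject prematurely discontinues the study, the reason for discontinuation should be documented in Case Report Form (CRF". The listed reasons are investigator judgment, non-compliance, loss to follow-up, the subject's own decision and death.

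Section 13.18 deals with subjects who have withdrawn. It states "Investigator will have to follow the patient who has been withdrawn from the study" and adds "In any case, every effort must be made to undertake protocol-specified safety follow-up procedures". Those who withdraw voluntarily are to be asked to keep attending and to have a final evaluation.

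Section 14.8 requires investigators to report all serious adverse events within 24 hours of occurrence and sets no end at exit.

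The safety endpoint in 12.5 is "Freedom from major adverse cardiac events (MACE) through hospital discharge and at one month". Its components are death, MI, target lesion revascularization, tamponade and life-threatening arrhythmia.

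**The concern.** For a subject who leaves early, 14.2 closes the reporting window while 13.18 asks the site to go on collecting safety information. A site that follows 14.2 literally has grounds not to record an MI or a target lesion revascularization that occurs after exit but before day 30. A site that follows 13.18 would record it. With up to five sites and 30 subjects, one event handled differently is visible in the reported rate.

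An analysis plan can say how a missing one-month MACE status is treated. It cannot restore an event that was never reported. The collection window is fixed in the protocol, so the ambiguity has to be removed there.

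**Working it through.** **Step 1: do the sections fit together?**

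| Section | Subject who leaves early |
|---|---|
| 14.2 | Reporting ends at exit |
| 13.16 | Exit section describes premature discontinuation; no date rule |
| 13.1 | Screen failures are exited once the failure is confirmed, so exit means the moment of leaving |
| 13.18 | Follow-up and safety procedures continue after withdrawal |
| 14.8 | All SAEs reported, no exit limit |

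Sections 14.2 and 13.18 agree only if exit is dated after the continued evaluations in 13.18. No sentence says so, and the use of the term in 13.1 and 13.16 points the other way.

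**Step 2: who is affected?** Section 15 gives a minimum of 25 patients and states "Considering the 5 dropouts, Sponsor has set up this protocol" for 30, and 25 + 5 = 30 reproduces its figure. Consent withdrawals before the index procedure are screen failures under 13.1: "These subjects will not be considered as part of the 30 patients for the analysis". The 5 are therefore plausibly losses after the procedure, or 5/30 = 16.7%. Two groups drop out of the problem:

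- deaths, because death is itself a listed exit reason;
- subjects truly lost, or refusing contact, who yield no data under any section.

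What remains is some of the 5.

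**Step 3: effect if exits stay in the denominator as event-free.** Rate = (30 − events)/30, with exact (Clopper-Pearson) 95% intervals. Two reported MACE are assumed for illustration.

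| Unreported events after exit | True MACE-free rate | 95% CI |
|---|---|---|
| 0 | 28/30 = 93.3% | 77.9 to 99.2 |
| 1 | 27/30 = 90.0% | 73.5 to 97.9 |
| 5 (bound) | 23/30 = 76.7% | 57.7 to 90.1 |

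The report would show 93.3% in every row. Each unreported event is worth 1/30 = 3.3 points, and the bound is 5/30 = 16.7 points.

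**Step 4: effect if the 5 exits are treated as missing.** The report would show 23/25 = 92.0%.

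- If none of the 5 had an event, full follow-up would give 28/30 = 93.3%, so the report is 1.3 points too low.
- If one did, full follow-up would give 27/30 = 90.0%, so the report is 2.0 points too high.

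**Step 5: how likely is an event among 5 subjects?** P(at least one) = 1 − (1 − p)^5. The protocol gives no MACE rate for this population, so p is an assumption.

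| Assumed p | P(at least one of 5) |
|---|---|
| 5% | 23% |
| 8.6% | 36% |
| 10% | 41% |
| 20% | 67% |

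The 8.6% is the rate section 9 cites from a study in acute MI, a different population; it implies 5 × 0.086 = 0.43 expected events. All of these overstate the loss, because events before exit are reported either way and fewer than 5 subjects may be affected.

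**The case against.** The strongest reply is that this is an undefined term, not a contradiction. Exit has no date. If it is placed at the final evaluation mentioned in 13.18, or at completion of the end-of-study form in 13.14, 14.2 and 13.18 agree. Section 13.18 is also the specific section on withdrawn patients, and a site would naturally turn to it. This reading is possible, but the protocol never states it, and a site has no rule for choosing it.

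The second reply carries more weight. Most MACE components would be serious adverse events, and 14.8 requires all of those to be reported without an exit limit. Section 13.13 provides for obtaining outside records when complications are treated elsewhere, and the synopsis has the one-month visit ask about coronary interventions since the last contact. A reader might infer from 14.2 alone that MACE after exit will be lost. The documents do not support that: 14.8 and 13.18 both give sites reason to report. What stands is that 14.2 is the sentence that sets a window, and it points the other way.

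Third, 13.18 is partly worded as effort or request, so it does not secure data on every withdrawn subject.

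Fourth, a reader might infer that omission can only flatter the device. That holds only if early exits are kept as event-free in a denominator of 30. If they are treated as missing, Step 4 shows that the reported rate can err either way.

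Finally, section 15 states no success threshold, so no decision is shown to change. The separate safety management plan mentioned in 14.8 may add detail, but it is not available here.

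**Conclusion.** The concern holds in a limited form. Section 14.2 conflicts with 13.18 and sits badly with 14.8, and nothing says which governs. The exposure is a MACE after exit and before one month, in a subject who left by investigator judgment, non-compliance or voluntary decision and can still be contacted.

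The size is some of 5 planned dropouts in 30, and 3.3 points per unreported event if the subject is counted as event-free. A reader might take 16.7 points as the likely error. It would require all five dropouts to have a MACE after leaving and every one to go unreported despite 13.18 and 14.8, so it is a theoretical bound only.

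This rests on reading exit as the moment of leaving and on the 5 dropouts falling after the procedure. It is worth correcting because the fix is small, but it does not undermine the study.

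**What to change.** Reword the one sentence in 14.2 so that adverse events are reported for every enrolled subject up to the one-month visit (30 ± 7 days), also after early exit, unless the subject refuses further follow-up, with a cross-reference to 13.18. Leave 13.18, 14.3 and 14.8 unchanged.

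The sample size stays at 30. No visit or form is added beyond what 13.18 already asks. The cost is recording events to one month for at most about 5 subjects at sites that would otherwise have stopped at exit.
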